16. ASSESSMENT OF IMMUNOGENICITY

All serum samples for neutralization titer determination will be handled according to the procedures supplied to each investigative site for the preparation, storage and shipment of samples (refer to Laboratory Manual). Each clinical study site will be responsible for the separation of serum from whole blood samples and the safe and controlled storage of serum samples prior to shipment to the central analytical laboratory.

At the end of the study, results of immunogenicity assessments will be provided to the Investigator.

Immunogenicity assessment measuring neutralizing antibodies will be performed on samples collected at Days 1, 8, 29 (Month 1), 85 (Month 3) and 180 (Month 6) after a single immunization.

16.1 Determination of vaccine-induced neutralizing antibody response

Immunogenicity of VLA1553 will be evaluated using a micro Plaque Reduction Neutralization Test (μPRNT), which is based on the same principle as a plaque reduction neutralization assay (PRNT), but allows testing with higher throughput. This assay differs from the μNT assay used for the assessment of neutralizing antibodies during Phase 1 clinical testing. Chikungunya virus neutralizing antibodies will be measured in the μPRNT using a serially passaged, live-attenuated CHIKV vaccine (CHIKV 181/25, TSI-GSD-218 or 181/clone 25) developed by the Walter Reed Army Institute of Research (WRAIR, US).

The CHIKV μPRNT evaluates the levels of antibodies that neutralize CHIKV infection of Vero cells in human serum samples.

Seven (7) two-fold serial dilutions of the de-complemented serum samples are prepared in round-bottom 96-well plates. CHIKV 181/25 at a target working dilution (to obtain 100 PFU/well) is added sequentially to the serum dilutions and incubated at 37°C and 5% CO₂ for 60 minutes. Serum-virus complexes are then transferred onto plates, previously seeded overnight with Vero cells, and incubated at 37°C and 5% CO₂ for 60 minutes. Then, the serum-virus complexes are removed and a virus maintenance medium containing 0.5% Methyl Cellulose is added to the wells, followed by an incubation of 17 ± 1 hours at 37°C and 5% CO₂. The following day, cells are fixed with 4% Paraformaldehyde for 15 minutes and permeabilized with 0.2% Triton X-100. Following cell permeabilization, indirect immunostaining is performed. Primary antibody diluted in blocking agent is added to the plates and incubated at 37°C for 60 minutes. Afterwards, the secondary antibody diluted in blocking agent is added to the plates and incubated at 37°C for 30 minutes. Substrate is

added to the plates and incubated for 10 minutes in the dark. Plates are rinsed with sterile water and left to be dried completely. Images from each well are acquired by an automated microscope system (ScanLab reader). The number of resulting PFUs in the wells is inversely proportional to the level of functional antibodies present in the serum, which is directly proportional to the immunological response of the subject.

The cut-off of CHIKV-specific neutralization antibody titer to be used in the analysis of seroconversion is defined as CHIKV-specific neutralizing antibody titer of [REDACTED] for baseline negative subjects. Seroconversion for baseline positive subjects is defined as a [REDACTED] increase over baseline.

16.2 Additional Testing Procedures

Serum samples obtained in this study may, in addition to its use for assessment of CHIKV-specific neutralizing antibody titers, also be used for further development of the vaccine, including but not limited to the following assays:

- Passive immunization assays to evaluate the potency of immune sera to protect animals from infection after wild-type challenge;
- Development of additional neutralization assays (e.g. μNT, PRNT, virus replicon particle neutralization assays) for the assessment of cross neutralization of heterologous CHIKV strains or other related (alpha) viruses;
- Detection of anti-CHIKV antibodies by enzyme linked immunosorbent assay (ELISA);
- Detection of viremia by viral culture;
- CHIKV sequencing;
- Clinical diagnostic work-up.

Such development may occur at laboratories other than the central analytical laboratory used for this study.

17. ASSESSMENT OF SAFETY

17.1 Definitions

17.1.1 Adverse Events

An adverse event (AE) is defined as any untoward medical occurrence in a subject administered an investigational product that does not necessarily have a causal relationship with the treatment. All new abnormalities or any exacerbation in intensity or frequency (worsening) of a pre-existing condition during or after vaccination have to be documented as AEs.

17.1.2 Serious Adverse Event

A **serious** adverse event (SAE) is defined as any untoward medical occurrence that at any dose meets one or more of the following criteria:

- Outcome is fatal/results in death (including fetal death);
- Is life-threatening – defined as an event in which the subject was, in the judgment of the Investigator, at risk of death at the time of the event; it does not refer to an event that hypothetically might have caused death had it been more severe;
- Requires inpatient hospitalization or results in prolongation of an existing hospitalization;
- Results in persistent or significant disability/incapacity (i.e., a substantial disruption of a person's ability to conduct normal life functions);
- Results in congenital anomaly/birth defect;
- Is a medically important condition – a medical event that may not be immediately life-threatening or result in death or require hospitalization but may jeopardize the subject or may require medical or surgical intervention to prevent one of the other outcomes listed in the definitions above. This definition also applies to progression of disease leading to a serious outcome.

In case of hospitalization or prolonged hospitalization for diagnostic or elective medical procedures that were planned prior to vaccination to treat a pre-existing condition that did not change in severity, neither the condition leading to the hospitalization or prolonged hospitalization, nor the medical procedure itself need to be reported as an SAE. In this case, the underlying diagnosis or condition should be reported in the medical history section of the eCRF and the corresponding medical procedure should be documented as a comment to the underlying diagnosis or condition in the eCRF's medical history section.

The Sponsor will classify the SAEs as either expected or unexpected:

- **Expected:** An AE that is listed in the current Investigator's Brochure (IB);
- **Unexpected:** An AE that is not listed in the current IB, or it differs because of greater severity or greater specificity.

For the purpose of this study, AEs graded as potentially life-threatening (Grade 4) (see Section 17.2.2 for solicited AEs) will be reported as SAEs.

17.1.3 Adverse Events of Special Interest

An AESI (serious or non-serious) is an event of scientific and medical concern specific to the Sponsor's product.

17.1.4 Medically-Attended Adverse Event

All AEs where subjects are seeking medical care (i.e. doctor's office, emergency service, hospital, but not including use of self-medication).

17.1.5 Preexisting Diseases

Preexisting diseases that are present before entry in to the study, that are described in the medical history, and that manifest with the same severity, frequency, or duration after vaccine exposure, will not be recorded as AEs. Furthermore, routine health checks required due to pre-existing diseases will not be recorded. However, when there is an increase in the severity of a preexisting disease, the event must be described on the AE CRF page.

17.1.6 Untoward Medical Occurrences Not Considered Adverse Events

Each untoward medical occurrence experienced before vaccine exposure (for example, from the time of signed informed consent up to but not including vaccine exposure) will be described in the medical history.

17.2 Collection, Documentation and Assessment of Adverse Events

17.2.1 Unsolicited Adverse Events

Subjects will be provided with an eDiary and eMemory Aid to collect unsolicited AEs occurring until the end of study (Visit 5, see Section 17.3). Additionally, the Investigator will enquire about AEs during study visits. Clinically relevant laboratory parameter changes constitute unsolicited AEs, too, unless they are considered a symptom of an underlying AE or part of a syndrome that is reported as AE (e.g. presence of blood cells in urine in a

person diagnosed with urinary tract infection). In addition, symptoms noted during the symptom-driven physical exams (unless already covered by an AE) constitute AEs.

All unsolicited AEs need to be documented in the respective AE section of the eCRF during applicable study visit (Visits 1 to 5 or unscheduled visit(s), if applicable), regardless of their source (AEs noted in the eMemory Aid (see Section 17.3), open question to subject, laboratory parameters, symptom-driven physical examination).

Any symptom is regarded as a separate AE. However, if the Investigator considers several symptoms to be in the context of one underlying diagnosis, the Investigator may merge these symptoms into one single appropriate AE. The AE term entered into the eCRF should contain all symptoms summarized to one event (e.g. "Influenza with flu-like-symptoms, fever and headache").

The Investigator will follow-up on each AE until it is resolved or until the medical condition of the subject is stable. All relevant follow-up information will be reported to the Sponsor until the end of the study for each subject. SAEs ongoing at the time of Visit 6 will be followed until resolution or achievement of stable clinical conditions, latest until the end of the study.

Beyond study end, if the investigator becomes aware of SAEs that are fatal, life-threatening or suspected to be related to study treatment will continue to be reported until 6 months after the last study visit of the respective subject (i.e., Visit 5).

The following information will be documented for each AE: severity, causality, outcome, seriousness, medically-attended, action taken to treat AE, start and stop dates.

17.2.1.1 Severity

The investigator will assess the severity of AEs using his/her clinical expertise and judgment based on the most appropriate description below:

Mild (Grade 1): Awareness of signs or symptoms, but easily tolerated, does not interfere with daily activities.

Moderate (Grade 2): Discomfort enough to interfere with usual activity and with or without requiring medical intervention.

Severe (Grade 3): Incapable of work or usual activity and requiring medical intervention.

17.2.1.2 Causality

Causality is a determination of whether there is a reasonable possibility that the vaccine administration is etiologically related to/associated with the AE.

For AEs, the Investigator will assess the causal relationship between the IMP and the AE using his/her clinical expertise and judgement according to the following most appropriate algorithm for the circumstances of the AE:

Probable: Reaction that follows a reasonable temporal sequence from administration of the IMP, or that follows a known or expected response pattern to the suspected treatment and that could not reasonably be explained by known characteristics of the subject's clinical state.

Possible: Reaction that follows a reasonable temporal sequence from administration of the IMP, or that follows a known or expected response pattern to the suspected treatment; but that could readily have been produced by a number of other factors.

Unlikely: Reports not following a reasonable temporal sequence from administration of the IMP; an event, which may have been produced by the subject's clinical state or by other environmental factors. A more likely alternative etiology exists.

Not related (unrelated): Events for which sufficient information exists to conclude that the etiology is unrelated to the IMP.

An alternative aetiology, especially COVID-19 related symptoms, should be taken into consideration for a thorough causality assessment by the Investigator. Current symptoms include fever or chills, cough, shortness of breath or difficulty breathing, fatigue, muscle or body aches, headache, new loss of taste or smell, sore throat, congestion or runny nose, nausea or vomiting, diarrhea. For latest case definitions please refer to CDC webpage (<https://www.cdc.gov/coronavirus/2019-ncov/symptoms-testing/symptoms.html>). These symptoms need to be documented in the eCRF.

AEs with a causality reported as probable or possible will be considered related to the IMP. AEs with missing causality assessment will be regarded as related unless further specified. All other AEs will be considered as not related to IMP.

17.2.1.3 Assessment and Outcome of Adverse Events

Each AE from vaccination until study completion/termination will be described on the AE eCRF (i.e., 1 AE per form) using the medical diagnosis (preferred), symptom, or sign, in standard medical terminology in order to avoid the use of vague, ambiguous, or colloquial expressions (see definition in Section 17.1.1). AEs will be evaluated by the Investigator for:

- Seriousness as defined in Section 17.1.2
- Severity as defined in Section 17.2.1.1
- Causal relationship to vaccine exposure as defined in Section 17.2.1.2

For each AE, the outcome will also be documented as either:

➤ recovering/resolving	➤ recovered/resolved
➤ recovered/resolved with sequelae	➤ not recovered/not resolved
➤ fatal	➤ unknown

If the severity rating for an ongoing AE changes before the event resolves, the AE will not be reported a second time. Instead the original AE entry will be revised. For purposes of data capture the highest severity rating during the course of a single AE will be the severity rating entered on the AE eCRF.

NOTE: A subject's death per se is not an event, but an outcome. The event which resulted in the subject's death must be fully documented and reported, regardless of being considered related to treatment or not.

17.2.2 Solicited Adverse Events

17.2.2.1 Injection Site Reaction – Measurement and Evaluation

Subjects will be provided with a measuring device to measure the size of any measurable injection site reaction that may develop after vaccination. The subject will be instructed on how to measure any such reactions over a period of 10 consecutive days starting on the day of vaccination along the longest diameter of the reaction area and record this measurement in the Subject eDiary. Injection site reactions include injection site pain, tenderness, erythema/redness, induration and swelling.

Injection site reactions will be rated based on the FDA Guidance on Toxicity Grading Scales as described in Table 17.2-1. Any grade 4 injection site reaction should be reported as an SAE (see Section 17.1.2).

Table 17.2-1
Grading of Injection Site Reactions – Vaccine Specific Criteria

Vaccine-specific Criteria	Mild (Grade 1)	Moderate (Grade 2)	Severe (Grade 3)	Potentially Life Threatening (Grade 4) ^c
Pain	Does not interfere with activity	Repeated use of non-narcotic pain reliever > 24 hours or interferes with activity	Any use of narcotic pain reliever or prevents daily activity	Emergency room (ER) visit or hospitalization
Tenderness	Mild discomfort to touch	Discomfort with movement	Significant discomfort at rest	ER visit or hospitalization
Erythema / Redness ^a	2.5 – 5.0 cm 0.98 – 1.96 inch	5.1 – 10.0 cm 1.97 – 3.94 inch	> 10.0 cm > 3.94 inch	Necrosis or exfoliative dermatitis
Induration / Swelling ^b	2.5 – 5.0 cm (0.98–1.96 inch) and does not interfere with activity	5.1– 10.0 cm (1.97 – 3.94 inch) or interferes with activity	> 10.0 cm (> 3.94 inch) or prevents daily activity	Necrosis

^a In addition to grading the measured local reactions at the greatest single diameter.

^b Induration / swelling should be evaluated and graded using the functional scale as well as the actual measurement.

^c Any Grade 4 injection site reaction will be reported as SAE, Grade 3 severity should be documented.

17.2.2.2 Systemic Reactions – Measurement and Evaluation

Systemic reactions include fever, nausea/vomiting, headache, fatigue, myalgia (muscle pain), arthralgia (joint pain) and rash will be reported in a standardized manner over a period of 10 consecutive days after vaccination.

Systemic reactions will be rated based on the FDA Guidance on Toxicity Grading Scales as described in Table 17.2-2. Any grade 4 systemic reaction should be reported as an SAE (see Section 17.1.2).

Table 17.2-2
Grading of Systemic Reactions – Vaccine Specific Criteria

Vaccine-specific Criteria	Mild (Grade 1)	Moderate (Grade 2)	Severe (Grade 3)	Potentially Life Threatening (Grade 4) ^d
Fever ^a	38.0 – 38.4 °C 100.4–101.1 °F	38.5 – 38.9 °C 101.2–102.0 °F	39.0 – 40.0 °C 102.1–104 °F	> 40.0 °C >104 °F
Nausea/vomiting	No interference with activity or 1 – 2 episodes/24 hours	Some interference with activity or > 2 episodes/24 hours	Prevents daily activity, requires outpatient IV hydration	ER visit or hospitalization for hypotensive shock
Headache	No interference with activity	Repeated use of non-narcotic pain reliever > 24 hours or some interference with activity	Significant; any use of narcotic pain reliever or prevents daily activity	ER visit or hospitalization
Fatigue	No interference with activity	Some interference with activity	Significant; prevents daily activity	ER visit or hospitalization
Myalgia	No interference with activity	Some interference with activity	Significant; prevents daily activity	ER visit or hospitalization
Arthralgia ^b	No interference with activity	Some interference with activity	Significant; prevents daily activity	ER visit or hospitalization
Rash ^c	Macules/papules covering <10% body surface area (BSA) with or without symptoms (e.g., pruritus, burning, tightness)	Macules/papules covering 10- 30% BSA with or without symptom (e.g., pruritus, burning, tightness); limiting instrumental activity of daily living	Macules/papules covering >30% BSA with or without associated symptoms; limiting self care activity of daily living	-

^a Oral temperature; no recent hot or cold beverages or smoking.

^b Symptom not described in FDA Toxicity Grading Scale.

^c Grading based on Common Terminology Criteria for Adverse Events (CTCAE), NIH, v4.03, 2010.

^d Any Grade 4 systemic reaction will be reported as SAE, Grade 3 severity should be documented.

17.2.2.3 Body Temperature Measurement

From vaccination (Day 1) until Day 11 after vaccination (i.e., the first 10 post-vaccination days including the day of vaccination), the subject should measure his/her body temperature orally once every evening, assessments by the subject should occur at the same time each day, starting approximately 8 hours after vaccination. To optimize the comparability of the documented body temperatures, all subjects will be provided with a digital oral thermometer and be instructed in its use. The subjects may keep the thermometer after study termination.

If fever (oral body temperature $\geq 38.0^{\circ}\text{C}/100.4^{\circ}\text{F}$) occurs, body temperature should be measured at least every 4 to 8 hours until it returns to normal ($< 38.0^{\circ}\text{C}/100.4^{\circ}\text{F}$). All body temperature measurements including the date and time should be recorded in the Subject eDiary (see Section 17.3). In case of fever, the subject should record all fever measurements in the diary including the first value that shows a return to normal body temperature.

Body temperature measurements from vaccination (Day 1) until Day 11 after vaccination (i.e., the first 10 post-vaccination days including the day of vaccination) will be transcribed automatically or by the Investigator into the eCRF. If more than one body temperature value is recorded in the diary for a given day, the highest daily temperature reading will be recorded in the eCRF.

Body temperature measurements will be analyzed according to the FDA Guidance on Toxicity Grading Scales for Healthy Adult and Adolescent Volunteers Enrolled in Preventive Vaccine Clinical Trials (Food and Drug Administration) for data analysis as described in **Table 15.2-2** above.

Outside of the first 10 post-vaccination days, daily body temperature measurement is **not required**. However, subjects experiencing an AE with symptoms of fever are recommended to measure their body temperature in order to document fever as an AE in the eMemory Aid. If fever (i.e., oral body temperature $\geq 38.0^{\circ}\text{C}/100.4^{\circ}\text{F}$) occurs, it is recommended that the subject measures his/her body temperature every 4 to 8 hours until fever resolves (i.e., oral body temperature $< 38.0^{\circ}\text{C}/100.4^{\circ}\text{F}$) in order to document onset and resolution, as defined by the date of first oral body temperature measurement of $\geq 38.0^{\circ}\text{C}/100.4^{\circ}\text{F}$ (date of onset) and the date of first oral body temperature measurement of $< 38.0^{\circ}\text{C}/100.4^{\circ}\text{F}$ (date of resolution).

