17.5 Vital Signs

Vital signs will include body temperature (°C / °F) measured orally, pulse rate (beats/min), and systolic and diastolic blood pressure (mmHg) while seated and at rest.

Vital signs will be measured at screening (Visit 0) and at the vaccination visit (Visit 1) and are to be recorded before the vaccination is given. In addition, after an observation period of 30 minutes at the study site following vaccination pulse rate as well as blood pressure while seated and at rest will again be assessed.

Vital sign values are to be recorded on the appropriate eCRF. For each vital sign value, the Investigator will determine whether the value is considered an AE (see definition in Section 17.1.1). If assessed as an AE, the medical diagnosis (preferably), symptom, or sign, will be recorded on the AE eCRF. Additional tests and other evaluations required to establish the significance or etiology of an abnormal result, or to monitor the course of an AE should be obtained when clinically indicated. Any abnormal value that persists should be followed at the discretion of the Investigator.

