17.9 Adverse Events of Special Interest (AESI)

In addition to nonspecific transient muscle pain and joint pain that may occur after vaccination with any vaccine, subjects will be carefully monitored for signs and symptoms suggesting an acute stage CHIKV-associated event.

If a subject develops symptoms suggestive of CHIKV infection, he/she will be asked to contact the site immediately for clinical evaluation at an unscheduled visit.

Therefore, the following cluster of symptoms with or without remissions or exacerbations will receive particular consideration:

1. Fever ($\geq 38.0^{\circ}\text{C} / 100.4^{\circ}\text{F}$ measured orally);

AND

2. Acute (poly)arthralgia/arthritis most frequently in the extremities (wrists, ankles and phalanges, often symmetric), back pain and/or neurological symptoms (e.g. confusion, optic neuritis, retinitis/uveitis meningoencephalitis or polyneuropathy) and/or cardiac symptoms (e.g. myocarditis);

OR

One or more of the following signs and symptoms: macular to maculopapular rash (sometimes with cutaneous pruritus (foot arch) and edema of the face and extremities), polyadenopathies;

AND

3. Onset of symptoms 2 to 21 days after vaccination;

AND

4. Duration of event ≥ 3 days.

Any suspected clinical case of CHIKV-associated event shall be referred to a clinical expert, be evaluated according to standard diagnostic procedures and treated according to current medical standard until resolved or stabilized. For more detailed information please refer to: French guidelines for the management of chikungunya - acute and persistent presentations (Simon, Javelle et al. 2015).

Additionally, subjects presenting with acute arthralgia within 2 to 21 days post-vaccination will be followed-up until resolution and monitored for recurrences until the end of the study.

A blood sample for laboratory investigation will be taken upon presentation of the subject. Testing may include but is not limited to rheumatoid factor (RF), anticitrullinated protein antibody (ACPA), Ferritin and CRP. Retrospective investigation of a pre-vaccination sample may be considered for a thorough causality assessment.

Suspected CHIKV-associated events do not constitute a reason for withdrawal from the study.

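### For 50–60% of the AESI onset window, the fever criterion rests on recommended self-measurement triggered only by symptoms of fever, so late-onset AESIs may be under-ascertained

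*Protocol*

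**What the plan says.** **Case definition.** Protocol Section 17.9 describes a cluster of symptoms, and Section 17.10.2 makes that cluster the AESI definition. Item 1 is fever of at least 38.0 °C, "measured orally". It is joined by AND to joint, back, neurological or cardiac symptoms, with an alternative limb that begins "One or more of the following signs and symptoms: macular to maculopapular rash". Two further conditions follow, each also joined by AND: "Onset of symptoms 2 to 21 days after vaccination" and "Duration of event ≥ 3 days". SAP Section 11.7.5 repeats this structure.

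**Temperature collection.** Section 17.2.2.3 asks for one oral reading every evening. It gives the period as "From vaccination (Day 1) until Day 11 after vaccination (i.e., the first 10 post-vaccination days including the day of vaccination"). It then says: "Outside of the first 10 post-vaccination days, daily body temperature measurement is" not required. For the later period, "subjects experiencing an AE with symptoms of fever are recommended to measure their body temperature", with repeat readings recommended if fever is found.

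**Where readings are recorded.** In Section 17.3 the eDiary content list has an oral temperature item. The eMemory Aid list, which covers the time after the eDiary, does not.

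**Visits.** Section 17.5 places vital signs at screening and Visit 1. Section 15.4.1 has no scheduled visit between Visit 2 (Day 8) and Visit 3 (Day 29). Section 17.9 asks a subject with symptoms suggestive of chikungunya to contact the site for an unscheduled visit, and Section 15.4.3 leaves the content of such a visit to discretion.

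**Endpoint.** AESI frequency and severity in the 2-to-21-day window is a named secondary safety endpoint (Protocol Section 12.3.2; SAP Section 9.3).

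**The concern.** One item of the case definition is a measured quantity, and the schedule stops requiring that measurement partway through the onset window. The later trigger is also narrower than the definition. It depends on the subject feeling feverish, while the other half of the cluster (joint pain, rash, nodes, neurological or cardiac symptoms) does not prompt a reading.

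At stake is how evenly the endpoint is ascertained. An early-onset event comes with a daily temperature series. A late-onset event may come with none unless the subject perceived fever, followed a recommendation, or was measured at an unscheduled visit. For a live-attenuated chikungunya vaccine, a reported AESI rate for the whole window should mean the same thing at both ends of it.

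**Working it through.** The documents state no figure for the uncovered share, so there is none to reproduce. The check is a day count followed by a comparison of sections.

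**Inputs**
- Vaccination is Study Day 1 (SAP Section 11.2), so day *k* after vaccination is Study Day *k* + 1.
- Onset window (Section 17.9), read literally: Study Days 3–22, which is 22 − 3 + 1 = 20 days. If Study Days 2–21 were meant: 21 − 2 + 1 = 20 days.
- Required daily temperature (Section 17.2.2.3): Days 1–11 is 11 calendar days. Ten days counting the vaccination day is Days 1–10. The section gives both as the same period.

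**Formula:** covered = last required day − first window day + 1; uncovered = 20 − covered.

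| Window (Study Days) | Last required day | Covered | Uncovered | Share |
|---|---|---|---|---|
| 3–22 | 11 | 11 − 3 + 1 = 9 | 11 | 55% |
| 3–22 | 10 | 10 − 3 + 1 = 8 | 12 | 60% |
| 2–21 | 11 | 11 − 2 + 1 = 10 | 10 | 50% |
| 2–21 | 10 | 10 − 2 + 1 = 9 | 11 | 55% |

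The uncovered share is 50–60% overall, and 55–60% on the literal reading of the window. Three of the four readings exceed half and one equals it.

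**What the text requires for the same symptom on two days**
- *Joint pain or rash starting on Day 8:* an evening reading is already required that day and on the following days.
- *Joint pain or rash starting on Day 14, without feeling feverish:* Section 17.2.2.3 neither requires nor recommends a reading. The eMemory Aid list has no temperature item. If the subject contacts the site under Section 17.9, a temperature may be taken at the unscheduled visit but is not mandated. Visit 3 has a window of ±4 days, so it falls on Day 29 − 4 = Day 25 at the earliest, after the onset window has closed. A reading not taken at the time cannot be recovered there.

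The Section 24.2 grid is not legible in the copy I worked from, so I relied on Sections 15.4 and 17.5. This does not change the result, because no scheduled visit falls in the gap.

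**Whether later steps recover a missed case.** Under SAP Section 11.7.5 only events flagged as AESIs on the CRF enter the AESI analysis, and the DSMB adjudicates cases already reported. Neither step finds a case that was never flagged.

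**The case against.** The strongest reply is that the protocol does not abandon temperature after Day 11. Every subject has a thermometer, and Section 17.2.2.3 recommends readings when fever is suspected, with onset and resolution dates documented. Section 17.9 brings suspected cases in for clinical evaluation. It also follows acute arthralgia in the window to resolution whether or not there is fever. The event would still be recorded as an AE, so only the AESI label is in doubt. All of this stands.

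It rules out several stronger readings that a reader might infer:
- *That fever goes unmeasured after Day 11, or that a subject with late joint pain is never asked for a temperature.* Measurement becomes recommended and symptom-triggered, and a site assessing a suspected case may well take one.
- *That a subject without a reading cannot be an AESI.* SAP Section 11.7.5 has the investigator identify AESIs with the list as a guideline. The AND/OR structure is also not bracketed, so on one reading fever is not needed for the rash or node limb. It remains an item for the joint, neurological and cardiac limb on either reading.
- *That 50–60% of cases are at risk.* The figure counts calendar days. Protocol Section 10.2.1 puts wild-type symptom onset usually at 4–7 days after infection. If vaccine-related events followed that timing, most would fall inside the daily-temperature period.
- *That the lot comparison is biased.* All arms receive VLA1553 on one blinded schedule.

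The reply does not remove the uneven standard. Using the list as a guideline does not supply a missing temperature. The investigator must either set the fever item aside or leave the event unflagged, and the protocol does not say which.

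**Conclusion.** The mismatch is real and modest. Required daily temperature ends at Day 10 or 11. For 10–12 of the 20 onset days, the fever item then depends on recommended self-measurement that AESI-type symptoms alone do not trigger. Late-onset AESIs may be under-ascertained relative to early-onset ones, and the likely direction is a lower absolute AESI rate.

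The size in cases cannot be derived from the documents. It depends on how many events start late, how often fever goes unnoticed, and how often sites measure it without being told to. The percentages assume only the day conventions shown in the table. Any loss should be similar across lots, and the Day 29 GMT analysis is not involved. This is a low-cost improvement to a named secondary safety endpoint.

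**What to change.** The change concerns data collection only.

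1. In Protocol Sections 17.2.2.3 and 17.3, require an oral temperature on any day from the end of the eDiary period to the end of the AESI window on which the subject records joint or back pain, rash, swollen nodes, or a neurological or cardiac symptom. Add an eMemory Aid field for the reading.
2. Require and record an oral temperature at any unscheduled visit for a suspected AESI (Sections 15.4.3 and 17.9).
3. Reconcile the Day 10 and Day 11 wording, and state the AESI window in Study Days in both documents.

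**Cost.** Subjects already have the thermometer and the eMemory Aid, so the added burden is slight. The change needs a protocol amendment with IRB approval (Section 19.2) and a revision of the electronic tool. Section 13.3 shows that screening had already taken place under protocol version 2.0, so ascertainment may differ between subjects followed before and after the amendment.

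Extending daily readings for everyone to the end of the window would also close the gap. It trades more burden for more sensitivity, which is the sponsor's judgement, and it is not needed to address this point.
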